6.2.3.5. Geometric mean titers (GMTs) and concentrations (GMCs)

GMT or GMC calculations are performed by taking the inverse logarithm of the mean of the log titer or concentration transformations. Non quantifiable antibody titers or concentrations will be converted as described in Section 6.2.3.4 for the purpose of GMT/GMC calculation. Cut-off values are defined by the laboratory before the analysis.

6.2.3.6. Onset day

The onset day for an event (e.g., AE, concomitant medication/vaccination) is the number of days between the last study dose and the start date of the event. This is 1 for an event occurring on the same day as a study dose (and reported as starting after study dose).

6.2.3.7. Duration of events

For the duration of solicited AEs:

- The duration of the event will be calculated as the sum of the individual days with the event reported as Grade 1 or higher or reported as missing during the solicited event period (see Section 6.2.2.3 for missing data). For Grade 3, the duration will be calculated as the sum of individual days with the event reported as Grade 3 or reported as missing during the solicited event period.

6.2.3.8. Counting rules for combining solicited and unsolicited adverse events

For output combining solicited and unsolicited adverse events, all serious adverse events will be considered systemic events since the administration site flag is not included in the expedited adverse event CRF pages. Unsolicited adverse events with missing administration site flag will also be considered systemic.

Solicited events will be coded by MedDRA as per the following codes:

Solicited event	Lower level term code	Corresponding Lower level term decode
Pain	10022086	Injection site pain
Erythema	10022061	Injection site erythema
Swelling	10053425	Injection site swelling
Fever	10016558	Fever
Headache	10019211	Headache
Fatigue	10016256	Fatigue
Myalgia	10028411	Myalgia
Arthralgia	10003239	Arthralgia

The latest available MedDRA version will be used for coding

Multiple events with the same preferred term which start on the same day are counted as only one occurrence.

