4.3.2. Safety analysis

The safety analysis will be performed on the ES as follows:

- The number and percentage of participants and doses with at least one administration site event AE (solicited and unsolicited), with at least one systemic AE (solicited and unsolicited) and with any AE during the 7-day (i.e., the day of vaccination and 6 subsequent days) and 30-day (i.e., the day of vaccination and 29 subsequent days) follow-up period will be tabulated with exact 95% CI after each dose and overall. The same computations will be done for Grade 3 AEs, for Grade 3 non-serious AEs and for AEs resulting in a medically attended visit.

These analyses will present all solicited and unsolicited AEs, including SAEs and pIMDs (unless otherwise specified).

The above analysis will also be performed for the solicited symptoms only during the 7-day (i.e., the day of vaccination and 6 subsequent days) follow-up period.

- The number and percentage of participants reporting each individual solicited administration site AE (any grade, Grade 3 and resulting in medically attended visit) and solicited systemic AE (any grade, Grade 3 and resulting in medically attended

visit) during the 7-day follow-up period (i.e., the day of vaccination and 6 subsequent days) will be tabulated for each group after each dose and overall. The percentage of doses followed by each individual solicited administration site AE (any grade, Grade 3 and resulting in medically attended visit) and solicited systemic AE (any grade, Grade 3 and resulting in medically attended visit) during the 7-day follow-up period (i.e., the day of vaccination and 6 subsequent days) will be tabulated, with exact 95% CI.

- For fever, the number and percentage of participants reporting fever by half degree (°C) cumulative increments during the 7-day follow-up period (i.e., the day of vaccination and 6 subsequent days) will be tabulated for each group after each dose and overall.
- The percentage of participants with each solicited administration site event and solicited systemic event (any grade and Grade 3) will be represented graphically for each group after each dose.
- The number of days with solicited events reported during the 7-day follow-up period (i.e., the day of vaccination and 6 subsequent days) will be tabulated for each individual solicited event using descriptive statistics (mean, minimum, Q1, median, Q3, maximum). The same computations will be done for Grade 3 solicited events.

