- The number of days with solicited events ongoing beyond the 7-day follow-up period (i.e., the day of vaccination and 6 subsequent days) will be tabulated for each individual solicited event using descriptive statistics (mean, minimum, Q1, median, Q3, maximum). The same computations will be done for Grade 3 solicited events.

All Analyses described above for solicited AEs will be also generated during only the 4-day follow-up period (i.e., the day of vaccination and 3 subsequent days).

- The number and percentage of participants with any unsolicited AEs during the 30-day follow-up period (i.e., the day of vaccination and 29 subsequent days) with its exact 95% CI will be tabulated by group and by Medical Dictionary for Regulatory Activities (MedDRA) System Organ Class (SOC), High Level Term (HLT) and Preferred Term (PT). Similar tabulation will be done for Grade 3 unsolicited AEs, for any causally related unsolicited AEs, for Grade 3 causally related unsolicited AEs and for unsolicited AEs resulting in a medically attended visit. The verbatim reports of unsolicited AEs will be reviewed by a physician and the signs and symptoms will be coded according to the MedDRA Dictionary for Adverse Reaction Terminology. Every verbatim term will be matched with the appropriate Preferred Term. The above analysis by dose will also be performed.

These analyses will present all unsolicited AEs, including SAEs and pIMDs (unless otherwise specified).

- The number and percentage of participants with at least one report of SAE classified by the MedDRA Primary SOC, HLT and PTs and reported after vaccine administration (Day 1) up to study end (6 months after last vaccination) will be tabulated with exact 95% CI.
- The number and percentage of participants with at least one report of causally related SAE classified by the MedDRA Primary SOC, HLT and PTs and reported after

vaccine administration (Day 1) up to study end (6 months after last vaccination) will be tabulated with exact 95% CI.

- The same tabulation will be presented for fatal SAEs.
- All SAEs will also be described in detail in a tabular listing.
- All pIMDs will also be described in detail in a tabular listing.
- All AEs/SAEs leading to study/intervention discontinuation from dose 1 up to study end will be tabulated.

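### In tables that combine solicited and unsolicited AEs, the SAP counts every SAE, and every unsolicited AE with a blank site flag, as systemic, so an injection-site SAE can fall in the wrong row

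*SAP*

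**What the plan says.** SAP 4.3.2 (Safety analysis) tabulates, on the Exposed Set, counts of both doses and participants in three overlapping categories: "with at least one administration site event AE (solicited and unsolicited), with at least one systemic AE (solicited and unsolicited) and with any AE". It does so over 7 and 30 days, after each dose and overall. It then adds: "The same computations will be done for Grade 3 AEs, for Grade 3 non-serious AEs and for AEs resulting in a medically attended visit". The section says that SAEs and pIMDs are included unless otherwise specified.

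SAP 6.2.3.8 supplies the rule that decides which row an event enters. Limited to output that pools the two kinds of event, it reads: "all serious adverse events will be considered systemic events since the administration site flag is not included in the expedited adverse event CRF pages". The reason given is thus one of data capture. A second rule follows: "Unsolicited adverse events with missing administration site flag will also be considered systemic".

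Both rules are introduced for combined output. SAP 4.3.2 separately plans a solicited-only version of the table, tables of each individual solicited event, tables of unsolicited AEs and of SAEs by MedDRA SOC, HLT and PT, and a detailed SAE listing. On coding of unsolicited AEs it says: "Every verbatim term will be matched with the appropriate Preferred Term".

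**The concern.** Whether a reaction is local or systemic is a property of the reaction. Here the row is decided by which CRF page the event was reported on. A serious reaction at the injection site is counted as systemic because the expedited page has no site field, even when its reported term names the site.

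The local/systemic split is a natural summary of what this trial compares. At Visit 1 the Co-Ad group receives two injections, one in each arm, and the Control group receives one (protocol Table 7 and section 4.1). Safety and reactogenicity of co-administration is a secondary objective. A reader who takes the combined table as the summary of local tolerability would not see that serious site reactions are assigned elsewhere by rule.

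The missing flag is also avoidable. SAEs are already tabulated by MedDRA term, and SAP 6.2.3.8 itself codes the three solicited local events to lower level terms that name the injection site.

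**Working it through.** The plan states no figure on this point, so there is none to reproduce. The check is to follow one event through the rows and then size the shift.

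**Step 1. Which outputs the rules reach.** They reach the combined administration-site, systemic and any-AE table and its Grade 3 and medically attended repeats. The Grade 3 non-serious repeat excludes SAEs by definition, so only the blank-flag rule can act there. The registry output in SAP 4.3.2 also combines solicited and unsolicited events, but it is restricted to non-serious events and laid out by SOC and PT, with no local/systemic row.

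**Step 2. What happens to one injection-site SAE.** Rows count participants (or doses) with at least one event, so the result depends on what else is recorded at that grade and in that window:

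| Other qualifying events | Administration-site row | Systemic row | Any-AE row |
|---|---|---|---|
| None | loses 1 | gains 1 | unchanged |
| Local only | unchanged | gains 1 | unchanged |
| Systemic only | loses 1 | unchanged | unchanged |
| Both | unchanged | unchanged | unchanged |

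**Step 3. Where another local event is less likely to keep the participant in the row.** Protocol 10.3.7.1 requires solicited events in the 7 days after each dose to be entered in the eDiary whatever their intensity. An eDiary entry of pain, redness or swelling therefore keeps the participant in the any-grade local row. Three situations weaken this:

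- In the Grade 3 table, a Grade 1 eDiary entry does not stand in for an SAE graded 3.
- In the medically attended table, a hospitalised site reaction qualifies (protocol 10.3.8.3 counts hospitalisation as medical attention). The participant stays in the local row only if another local event was also medically attended.
- In the 30-day table, a solicited-type symptom that starts after the solicited period is reported as unsolicited (protocol glossary), so there may be no eDiary record of it.

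**Step 4. Size.** Input: 514 planned participants per group (SAP section 5), all assumed vaccinated.

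- One case: 1/514 = 0.19 percentage points in an affected participant row.
- Five cases: 5/514 = 0.97 percentage points.
- If the case were the only local event in the row, the row would show 0/514 (0%, exact 95% CI 0 to 0.72%) instead of 1/514 (0.19%, exact 95% CI 0.00 to 1.08%). The intervals are Clopper-Pearson, the SAP's method for proportions.

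The documents give neither an expected number of injection-site SAEs nor a rate of blank site flags, so the numbers of cases above are illustrations only.

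**The case against.** The case for leaving the rule alone is substantial. It is pre-specified, disclosed, explained by the CRF structure and identical in both groups. None of the safety endpoints in SAP 1.1 is a combined local or systemic row: they are individual solicited events, unsolicited AEs, SAEs and pIMDs. The tables are descriptive, and an injection-site SAE remains visible in the any-AE row, the SAE table by preferred term and the SAE listing. All of this stands, and it keeps the point minor.

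A reader might also infer more than the documents support:

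- *That the SAP treats every SAE as systemic throughout.* It does so only in output that combines solicited and unsolicited events.
- *That both rows are wrong whenever such an event occurs.* Step 2 shows that either row, or both, can be unchanged.
- *That the rule strips out the most severe local reactions.* Protocol 10.3.8.1 separates seriousness from Grade 3 intensity, so an SAE need not be Grade 3.
- *That Grade 3 local rows are understated by some sizeable relative amount.* Any such figure needs an assumed row count, an SAE graded 3, and no other Grade 3 local event in that participant. The documents supply none of these.

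A last objection is that coding from the term is imperfect: a report that names an arm but not the injection site may not code to a site term. This is true. With systemic as the default, however, such an event is classified just as it is now, so the change makes nothing worse apart from rare miscoding. The objection limits the gain from the fix and does not argue against it.

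**Conclusion.** The concern holds within narrow limits. In the combined tables and their Grade 3 and medically attended repeats, a stated rule can place a recognisable injection-site SAE in the systemic row for a reason of data capture alone. The blank-flag rule can do the same to a non-serious unsolicited AE, including in the Grade 3 non-serious rows.

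The effect is at most 0.19 percentage points per case in a participant row, given 514 vaccinated per group. The local row loses the case only if the participant or dose has no other qualifying local event. The systemic row gains it only if there is no other qualifying systemic event. The number of cases is unknown from the documents and is presumably small. No hypothesis, power figure or primary analysis depends on the rule. This is an inexpensive improvement to a descriptive table and not a defect in the trial's safety assessment.

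**What to change.** In SAP 6.2.3.8, replace the two default rules with one: SAEs, and unsolicited AEs with a missing site flag, are classified as administration-site events when their coded MedDRA term denotes an administration, injection or vaccination site reaction, and otherwise as systemic. Fix the list of qualifying terms before database lock. Add a footnote to the combined tables saying how SAEs and blank-flag events were assigned.

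The cost is a short term list, a sentence in the SAP and a few lines of programming on data that will be coded anyway. It needs no new data, CRF change or protocol amendment. What remains is that events whose reported wording does not mention the site stay in the systemic row, and the footnote should say so.

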6.2.3.9. Counting rules for occurrences of solicited events

When the occurrences of solicited events are summarized, each event recorded as having occurred during a specific period will be counted as only one occurrence regardless of the number of days on which it occurs. Also, in the case of co-administered study interventions, an administration site event recorded for a participant following multiple study interventions will be counted as only one occurrence.

Table 5 Intensity grading scale for solicited events

Event	Intensity Grade	Parameter
Pain at administration site	0	None
	1	Mild: Any pain neither interfering with nor preventing normal everyday activities.
	2	Moderate: Painful when limb is moved and interferes with everyday activities.
	3	Severe: Significant pain at rest. Prevents normal everyday activities.
Erythema at administration site		Greatest surface diameter in mm
Swelling at administration site		Greatest surface diameter in mm
Temperature*		Temperature in °C.
Headache	0	None
	1	Mild: Headache that is easily tolerated
	2	Moderate: Headache that interferes with normal activity
	3	Severe: Headache that prevents normal activity
Fatigue	0	None
	1	Mild: Fatigue that is easily tolerated
	2	Moderate: Fatigue that interferes with normal activity
	3	Severe: Fatigue that prevents normal activity
Myalgia	0	None
	1	Mild: Myalgia that is easily tolerated
	2	Moderate: Myalgia that interferes with normal activity
	3	Severe: Myalgia that prevents normal activity
Arthralgia	0	None
	1	Mild: Arthralgia that is easily tolerated
	2	Moderate: Arthralgia that interferes with normal activity
	3	Severe: Arthralgia that prevents normal activity

The route for measuring temperature can be oral or axillary. Fever is defined as temperature $\geq 38.0^{\circ}\text{C}$ regardless of the location of measurement.

The maximum intensity of local injection site erythema/swelling, and fever will be scored at GSK as follows:

	Erythema/swelling	Fever
0:	$\leq 20\text{mm}$	$< 38.0^{\circ}\text{C}$
1:	$> 20 - \leq 50\text{mm}$	$\geq 38.0^{\circ}\text{C} - \leq 38.5^{\circ}\text{C}$
2:	$> 50 - \leq 100\text{mm}$	$> 38.5^{\circ}\text{C} - \leq 39.0^{\circ}\text{C}$
3:	$> 100\text{mm}$	$> 39.0^{\circ}\text{C}$

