
 To evaluate the safety and reactogenicity following administration of the RSVPreF3 OA investigational vaccine and the FLU vaccine, co-administered or administered alone. 	
 Percentage of participants reporting each solicited event with onset within 7 days after vaccine administration (i.e., the day of vaccination and 6 subsequent days). Percentage of participants reporting unsolicited AEs (pIMD, non-serious AE or serious AE) within 30 days after vaccine administration (i.e., the day of vaccination and 29 subsequent days). Percentage of participants reporting SAEs after vaccine administration (Day 1) up to study end (6 months after last vaccination). Percentage of participants reporting pIMDs after vaccine administration (Day 1) up to study end (6 months after last vaccination).

CCI

FLU vaccine refers to FLU aQIV

AE = adverse event; CCI = ; GMT = geometric mean titer; HI = hemagglutination inhibition; MGI = mean geometric increase; RSVPreF3 OA = respiratory syncytial virus PreFusion protein 3 older adult; SAE = serious adverse event; SCR = seroconversion rate; SPR = seroprotection rate; pIMD = potential immune-mediated disease; SCR = percentage of vaccinees who have either a HI pre-dose titer $< 1:10$ and a post-dose titer $\geq 1:40$ or a pre-dose titer $\geq 1:10$ and at least a 4-fold increase in post-dose titer.

SPR = percentage of vaccinees with a serum HI titer $\geq 1:40$ that usually is accepted as indicating protection.

[figure not shown]
MGI = geometric mean of the within-participant ratios of the post-dose titer over the pre-dose titer.

Details related to attributes of estimands covering intercurrent events, population and treatment definition are provided in Section 9.

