6.1. Study interventions administered

Table 7 Study interventions administered

Study Intervention Name:	RSVPreF3 OA Investigational Vaccine		FLU aQIV (adjuvanted quadrivalent influenza vaccine)**
Formulation:	RSVPreF3 (120 µg)	AS01 _E : QS-21* (25 µg), MPL (25 µg), liposomes; Water for injections	A/(H1N1) (15 µg HA)***; A/(H3N2) (15 µg HA)***; B/(Victoria Lineage) (15 µg HA)***; B/(Yamagata Lineage) (15 µg HA)***; adjuvanted with MF59C.1 (Squalene (9.75 mg), Polysorbate 80 (1.175 mg), Sorbitan trioleate (1.175 mg)); Water for injections
Presentation:	Vial; powder for suspension for injection	Vial; suspension for suspension for injection	Syringe: Suspension for injection
Product category:	Biologic		Biologic
Route of administration:	Intramuscular		Intramuscular
Administration site:			
Location	Deltoid		Deltoid
Directionality	Upper		Upper
Laterality	Non-dominant		Co-Ad group: Dominant Control group: Non-dominant
No of Doses:	1		1
Dose Volume[†]:	0.5 mL		0.5 mL
Packaging, labeling & TM:	Refer to the SPM for more details		
Manufacturer:	GSK	Seqirus, Inc.	

AS01_E = Adjuvant System 01; **Co-Ad** = co-administration; **HA** = Hemagglutinin; **MPL** = monophosphoryl lipid A; **QS-21** = *Quillaja saponaria* Molina, fraction 21; **RSVPreF3 OA** = respiratory syncytial virus PreFusion protein 3 older adult; **SPM** = Study Procedures Manual

*Licensed by GSK from Antigenics Inc, a wholly owned subsidiary of Agenus Inc., a Delaware, USA corporation.

**FLU aQIV (adjuvanted quadrivalent influenza vaccine) is marketed by Seqirus as *Fluad Tetra*, *FLUAD QUADRIVALENT* and *Fluad Quad*

***The vaccine strains recommended by the World Health Organization for the 2022/2023 northern hemisphere influenza season are: an A/Victoria/2570/2019 (H1N1)pdm09-like virus, an A/Darwin/9/2021 (H3N2)-like virus, a B/Austria/1359417/2021 (B/Victoria lineage)-like virus and a B/Phuket/3073/2013 (B/Yamagata lineage)-like virus.

[†] Refer to the Study Procedures Manual for the volume after reconstitution.

Study participants must be observed closely for at least 30 minutes after the administration of the study interventions. Appropriate medical treatment must be readily available during the observation period in case of anaphylaxis or syncope.

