1.2. Study Design

Overview of Study Design and Key Features	

Randomization 1:1 Total N = ~1028
 
Visit Timepoint
 
Co-Ad group N = ~514
 
Control group N = ~514
 
Vaccination Phase
 
Visit 1 Day 1
 
Visit 2 Day 31
 
CC1
 
Visit 4 Day 61
 
Contact 1 6 months post-last vaccination
 
RSV + flu vaccines
 
Flu vaccine
 
RSV vaccine
 
Safety monitoring
 
Solicited AEs up to 7 days post-dosing Unsolicited AEs up to 30 days post-dosing All SAEs and pIMDs up to study end SAEs related to study participation or to a concurrent GSK medication/vaccine up to study end AEs/SAEs leading to withdrawal from the study up to study end
 
CC1 : Blood sample (10 ml each visit for humoral immunogenicity)
 
CC1 : Contact with the participant (via phone, email, ...)
 
Visit CCI & CC1 Day 61 not applicable for the Co-Ad group
	
Vaccination Phase
 
Safety Follow-up
 
Safety monitoring
 
AE = adverse event; N = number of participants; pIMD = potential immune-mediated disease; RSV = respiratory syncytial virus; SAE = serious adverse event

Design Features
 
 Type of study: self-contained. Experimental design: Phase III, randomized (ratio 1:1), open-label, multi-country study with 2 parallel groups. Study groups: 
 Co-Ad (co-administration) group: Participants receiving the RSVPreF3 OA investigational vaccine co-administered with FLU aQIV (referred to as FLU vaccine). Control group: Participants receiving the FLU aQIV (referred to as FLU vaccine) and the RSVPreF3 OA investigational vaccine in a sequential manner. Duration of the study: ~6 months for participants in Co-Ad group; ~7 months for participants in Control group. Primary completion date: Day 61 (1 month after the RSVPreF3 OA investigational vaccine dose in Control group). Control: active comparator, i.e., sequential administration of licensed FLU vaccine and RSVPreF3 OA investigational vaccine. Blinding: open-label. Vaccination schedule: 
 Co-Ad group: Participants will be receiving both the RSVPreF3 OA investigational vaccine and FLU vaccine at Visit 1 (Day 1). Control group: Participants will be receiving the FLU vaccine at Visit 1 (Day 1) and subsequently the RSVPreF3 OA investigational vaccine at Visit 2 (Day 31). 	
Final analysis
 
End-of-Study analysis

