	
In the case of COVID-19 vaccines, this time window can be decreased to 14 days before and after each study intervention administration provided this COVID-19 vaccine use is in line with local governmental recommendations.
 
Note: In case an emergency mass vaccination for an unforeseen public health threat (e.g., a pandemic) is recommended and/or organized by the public health authorities, outside the routine immunization program, the time period described above can be reduced if necessary for that vaccine provided it is used according to the local governmental recommendations and that the Sponsor is notified accordingly.
			
1050	
Randomization failure:
 
Participant not randomized in the correct group (To be attributed by Statistician only; Check SBIR, replacement, vaccine administration)
	Visit 1	All	PPS for analysis of immunogenicity
1070	
Vaccine administration not according to protocol
 
Incomplete vaccination course
 
Participant was vaccinated with the correct vaccine but containing a lower volume
 
Wrong replacement or study vaccine administered (not compatible with the vaccine regimen associated to the treatment number)
 
Route of the study vaccine is not intramuscular
 
Side of administration wrong (for Co-ad group if both vaccines are given in the same arm)
 
Wrong reconstitution of administered vaccine
	Vaccination visit(s) 1 or 1 and 2 as applicable	From the specific visit (1 or 2) the condition is met as applicable for the respective group/antigen	PPS for analysis of immunogenicity
1080	
Vaccine temperature deviation
 
Vaccine administered despite a GMP no-go temperature deviation
	Vaccination visit(s) 1 or 1 and 2 as applicable	From the specific visit (1 or 2) the condition is met as applicable for the respective group/antigen	PPS for analysis of immunogenicity
1090	
Expired vaccine administered
	Vaccination visit(s) 1 or 1 and 2 as applicable	From the specific visit (1 or 2) the condition is met as applicable for the respective group/antigen	PPS for analysis of immunogenicity
2010	
Protocol violation linked to inclusion/exclusion criteria
	Visit 1,2 for the Co-ad group.	From the specific visit (1,2,3* or 4)	PPS for analysis of immunogenicity

Code	Condition under which the code is used	Visit /Contact(timepoints) where the code is checked	Visit from when it is applicable	Applicable for analysis set/endpoint

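### No solicited local-reaction table is planned by vaccine or injection site, so the by-dose rows set two Co-Ad sites against one Control site and no display compares either vaccine's local reactions with and without co-administration

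*SAP*

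**What the plan says.** The secondary safety objective (Protocol Section 3, Table 5) is "To evaluate the safety and reactogenicity following administration of the RSVPreF3 OA investigational vaccine and the FLU vaccine, co-administered or administered alone". Its reactogenicity endpoint is the share of participants with each solicited event in the 7 days after vaccination; the endpoint names neither a vaccine nor an injection site.

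Co-Ad participants receive both vaccines at Visit 1. Control participants receive FLU at Visit 1 and RSV at Visit 2, about a month later. Protocol Section 6.1, Table 7 puts RSV in the non-dominant arm in both groups. For FLU the entry is "Co-Ad group: Dominant Control group: Non-dominant". The SAP's per-protocol elimination codes (Section 3.1.2, code 1070) list giving both Co-Ad vaccines in one arm as an administration error.

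SAP 4.3.2 tabulates each solicited local event by group, after each dose and overall, as a share of participants. It adds a second measure: "The percentage of doses followed by each individual solicited administration site AE". The repeat by age group has the same participant layout. SAP 6.2.1 attributes an event to the most recent dose. SAP 6.2.3.9 sets the counting rule after co-administration: "an administration site event recorded for a participant following multiple study interventions will be counted as only one occurrence".

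**The concern.** Because the two Co-Ad injections go in opposite arms, a local reaction can in principle be traced to one vaccine. The planned tables do not use this. Attribution by timing cannot separate two injections given on the same day, and the counting rule merges them. The Co-Ad dose 1 row is then the chance of a reaction at either of two sites, whereas each Control row is the chance at one site.

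Two readings are at stake. The by-dose rows may show a Co-Ad excess that reflects only the number of injections. And a real rise at one site may be diluted in the overall row, which is the only row with two injections on each side.

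**Working it through.** **Figure to reproduce.** None. Neither document states a local reaction rate, so the rates below are assumptions for illustration.

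**Inputs.** Injections per dose visit: two in Co-Ad, one in Control (SAP 1.2). One collapsed occurrence per co-administration (SAP 6.2.3.9). Group size 514 (SAP 5). Assumed site rates *a* (RSV) and *b* (FLU), unchanged by co-administration.

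**Formulas.**
- Co-Ad dose 1, either site: *a* + *b* − P(both). With full overlap this is max(*a*, *b*); with independent sites it is *a* + *b* − *ab*. Negative dependence could push it higher, up to min(1, *a* + *b*).
- Control, percentage of doses: (*a* + *b*)/2, if everyone receives both doses.
- Co-Ad, percentage of doses: the either-site rate if a co-administration visit is one dose; half of it if the visit is two doses with one collapsed event.

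**By-dose rows, *a* = 60%, *b* = 40%.** Full overlap gives 60%; independence gives 0.60 + 0.40 − 0.24 = 76%. Control reads 40% after FLU and 60% after RSV. The Co-Ad excess is 0–16 points over the RSV dose and 20–36 points over the FLU dose, with no interference.

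**Percentage of doses, same rates.** Control: (60 + 40)/2 = 50%. Co-Ad: 60–76% with one dose per visit, or 60/2 to 76/2 = 30–38% with two. The direction of the difference depends on which is meant.

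**Other assumed rates** (full overlap to independence):

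| RSV / FLU | Co-Ad dose 1 | Above Control RSV | Above Control FLU | % of doses, one per visit | % of doses, two per visit | Control % of doses |
|---|---|---|---|---|---|---|
| 60 / 40 | 60–76 | 0–16 | 20–36 | 60–76 | 30–38 | 50 |
| 50 / 30 | 50–65 | 0–15 | 20–35 | 50–65 | 25–32.5 | 40 |
| 40 / 20 | 40–52 | 0–12 | 20–32 | 40–52 | 20–26 | 30 |

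**Precision.** For 76% against 60% with 514 per group, the 95% half-width is 1.96 × √[(0.76×0.24 + 0.60×0.40)/514] ≈ 5.6 points. An artefact at the upper end would look like a clear difference.

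**Dilution in the overall row.** Suppose co-administration raises the FLU-site rate from 40% to 50%, with sites independent in both groups. Overall row: 1 − 0.40×0.50 = 80% against 76%, which is 4 points with half-width 1.96 × √[(0.80×0.20 + 0.76×0.24)/514] ≈ 5.1. By site: 50% against 40%, which is 10 points with half-width 1.96 × √[(0.25 + 0.24)/514] ≈ 6.1. With full overlap in both groups, the overall row shows 60% against 60%.

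**Attribution.** Under independence, site rates of 60%/30%, 50%/44% and 70%/6.7% all give an either-site rate of about 72%. The collapsed figure does not recover the two rates.

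**The case against.** The strongest reply is that the counting rule suits the stated endpoint. A percentage of participants counts each person once, however many sites react, and this is equally true of the by-dose and overall rows. The overall row compares two injections with two, which is a fair comparison of regimens, and the endpoint does not promise attribution to one vaccine. All of this stands. The one-occurrence rule is not itself an error; what is missing is a table by vaccine or site.

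A reader might infer that the by-dose rows must show more reactions in Co-Ad. They need not: with full overlap, Co-Ad and the Control RSV dose both read 60%. A reader might also infer that the percentage of doses is biased upward. The SAP does not support this, because it does not say whether a co-administration visit is one dose or two. Protocol Section 4.2 speaks of a dose of each vaccine at that visit, while Protocol Table 13 labels the next sample as following dose 1.

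Nor are the tables wholly uninformative. Sampling error aside, the either-site rate is an upper bound for each site, so a Co-Ad rate no higher than a Control single-dose rate argues against a rise for that vaccine. A rate above the sum of the two Control rates would imply a rise in at least one. Between these bounds the tables do not settle the question.

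Finally, separate recording of each arm is not proven. The counting rule implies records per intervention, but the diary question shown in SAP 6.2.2.3 refers to a single site.

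**Conclusion.** The point holds as a gap in the planned displays. By-dose local rates are not like-for-like between groups, the percentage of doses is not like-for-like under either denominator, and no visible table compares each vaccine's local reactions when co-administered with those when given alone. At assumed rates of 60% and 40% without interference, the by-dose difference is 0–16 points against Control RSV and 20–36 against Control FLU. These sizes rest on assumed rates and on overlap between full and independent.

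The consequence is limited to interpretation of a descriptive secondary objective. No hypothesis test, margin, alpha or sample size is affected. SAP 4.3.2 shows no redaction; the redacted exploratory section (SAP 4.4) could not be checked.

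**What to change.** 1. In SAP 4.3.2, add a descriptive table of each solicited local event by vaccine and injection site, any grade and Grade 3: Co-Ad RSV site against Control RSV dose, and Co-Ad FLU site against Control FLU dose. Use the per-intervention diary records that SAP 6.2.3.9 implies.
2. Confirm first that the diary records each arm. If it does not, state in the SAP that by-dose local rates are not comparable between groups.
3. Keep the one-occurrence rule for every per-participant percentage, by dose and overall.
4. For the percentage of doses with local events, count injections in both numerator and denominator in both groups. In the 60%/40% illustration this gives (60 + 40)/2 = 50% in each group. This step also needs records by arm.
5. Footnote that the FLU comparison is confounded with arm (dominant in Co-Ad, non-dominant in Control), while RSV is given in the non-dominant arm in both.

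The cost is one or two extra descriptive tables and a short SAP edit. If each arm is already recorded, no new data are needed.
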